Neutropenia/ Febrile Neutropenia/ Anemia/ Pancytopenia	
Assess for other causes. Hold concomitant medications associated with myelosuppression.
 
Grade 3 neutropenia: Hold RMC-4630 if clinically indicated until the event recovers to Grade 1 or within normal limits or returns to baseline. If improvement occurs within 3 weeks, restart RMC-4630 at one dose level lower. If there is no improvement within 3 weeks, or upon recurrence of Grade 3 neutropenia, additional dose reduction of RMC-4630 or permanent discontinuation of RMC-4630 can be considered.
 
Grade 3 febrile neutropenia: Hold RMC-4630 and sotorasib until fever resolves and ANC recovers to Grade 1 or is within normal limits or returns to baseline. If improvement occurs within 2 weeks, restart RMC-4630 one dose level lower. If there is no improvement within 2 weeks, discontinue RMC-4630 and sotorasib.
 
Grade 3 anemia: Assess transfusion history. Transfuse per institutional guidelines. Hold RMC-4630 if clinically indicated until the event recovers to Grade 1 or within normal limits or returns to baseline. If improvement occurs within 4 weeks, restart RMC-4630 at the same dose level. If the AE re-occurs, consider dose reduction to one dose level lower for RMC-4630 after the AE resolves to Grade 1 or within normal limits or returns to baseline. If the AE does not improve within 4 weeks, consider discontinuation of RMC-4630.
 
Grade 4 pancytopenia: Hold RMC-4630 and sotorasib until resolves to Grade 1, within normal limits or returns to baseline. If improvement occurs within 4 weeks, restart RMC 4630 and sotorasib one dose level lower. If there is no improvement within 4 weeks, discontinue both drugs.

Table 6: Dose Modification Guidelines for RMC-4630 and Sotorasib (Continued)

AE	Action

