Diarrhea/ Nausea/ Vomiting	
Grade 1-2: Maximal supportive care. Continue both components of study treatment at current doses and ongoing prophylaxis maybe considered upon investigator's discretion after the first event
 
Grade 3: Hold both components of study treatment (if receiving maximal supportive care) until the event recovers to Grade 1 or normal or returns to baseline. If improves within 3 weeks, then restart RMC-4630 and sotorasib at 1 dose level lower. If not resolved within 3 weeks, permanently discontinue RMC-4630. If event recurs, hold both components of study treatment and consider a second dose reduction for both components of study treatment or permanent discontinuation of one or both components of study treatment depending on the clinical benefit. Note: Only one dose reduction is applicable for subjects starting dosing at 240 mg of sotorasib.
 
Grade 4: Permanently discontinue RMC-4630 and sotorasib for Grade 4 diarrhea or vomiting

Table 6: Dose Modification Guidelines for RMC-4630 and Sotorasib (Continued)

AE	Action

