Liver function tests (AST, ALT, and/or total bilirubin)	
Grade 1: Continue both components of study treatment at current doses.
 
Grade 2 AST or ALT with symptoms OR Grade 3 to 4 AST or ALT elevation: Rule out other causes such as metastatic liver disease, concomitant drugs, infection, hepatitis etc. Hold both RMC-4630 and sotorasib until the event recovers to Grade 1 or within normal limits or returns to baseline, then dose reduce RMC-4630 and sotorasib to one dose level lower. If AE does not improve or recurs, dose reduce another dose level. No dose modification is required for isolated elevations of GGT. Note: Only one dose reduction is applicable for subjects starting dosing at 240 mg of sotorasib.
 
Both components of study treatment should be permanently discontinued for concurrent elevation of AST or ALT $>3 \times$ ULN AND total bilirubin $>2 \times$ ULN or INR >1.5 in the absence of cholestasis and other causes (eg, viral hepatitis, other pre-existing or acute liver disease, or another drug capable of the observed injury), which may indicate severe DILI (potential Hy's law case). If liver injury is due to other causes such as viral hepatitis, acute liver disease, or another drug capable of liver injury, evaluate the extent of liver injury (eg, albumin level, PTT, INR, etc) and if considered to be severe, either consider continuing at a lower dose for both components of study treatment or discontinue one or both components of study treatment.

Hypertension	
Grade 2: Treat according to institutional/provider guidelines in accordance with goal of reduction to Grade 1 or baseline. Continue RMC-4630 and sotorasib.
 
Grade 3: Treat according to institutional guidelines with the goal of reducing blood pressure to Grade 1 or within normal limits or baseline. Consider holding RMC-4630. If there is improvement, restart RMC-4630 at the same dose level or one dose level lower per investigator judgement.
 
Grade 4: Treat according to institutional guidelines. Permanently discontinue RMC-4630.

ILD / pneumonitis	
Any Grade
 
Withhold RMC-4630 and sotorasib if ILD/pneumonitis is suspected.
 
If diagnosis is confirmed, permanently discontinue sotorasib and RMC-4630.

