8.4. Dose Limiting Toxicity Criteria

Potential DLTs are defined as all AEs specified below that occur during the first cycle of study treatment and that are considered by the investigator to be related to RMC-4630 and/or sotorasib.

DLT criteria are outlined below as follows:

- An AE that results in permanent discontinuation of RMC-4630 or sotorasib
- An AE that results in a delay of > 2 weeks in the start of Cycle 2
- Febrile neutropenia
- Grade 4 neutropenia of any duration
- Grade 3 neutropenia lasting >7 days
- Grade 3 thrombocytopenia with Grade ≥ 2 bleeding
- Grade 4 thrombocytopenia
- Grade 4 anemia
- Grade ≥ 4 vomiting and diarrhea

- Grade 3 vomiting or diarrhea lasting >3 days despite optimal medical support
- Grade ≥ 3 nausea lasting 3 days or more, despite optimal medical support
- Grade ≥ 3 rash lasting 3 days or more despite optimal medical support
- Grade 3 AST or ALT elevation lasting >5 days or Grade ≥ 4 AST or ALT elevation of any duration
- Grade ≥ 3 bilirubin elevation
- Grade ≥ 3 QTc prolongation
- Retinal vein occlusion
- Any other Grade ≥ 3 AE with the following exceptions:
 - Grade 3 Fatigue lasting 7 days or less
 - Asymptomatic Grade 3 electrolyte abnormalities that last <72 hours, are not clinically complicated, and resolve spontaneously or respond to medical interventions
 - Grade 3 amylase or lipase that is not associated with symptoms or clinical manifestations of pancreatitis
 - Other select laboratory abnormalities that do not appear to be clinically relevant or harmful to the subject and/or can be corrected with replacement or modifications (eg, Grade 3 lymphopenia, Grade 3 hypoalbuminemia)
- Any subject meeting the criteria for a Hy's Law case (ie, severe DILI) will be considered a DLT. A Hy's Law case is defined as the following: AST or ALT values of $\geq 3 \times$ ULN, AND total bilirubin $>2 \times$ ULN or INR >1.5 in the absence of cholestasis and other causes (eg, viral hepatitis, other preexisting or acute liver disease, or another drug capable of the observed injury), to explain the observed liver related laboratory abnormalities.

If a subject experiences a DLT during the DLT evaluation period during Cycle 1 of the safety run-in period, sotorasib and/or RMC-4630 treatment should be modified according to [Table 6](#) and [Table 7](#).

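### The Table 6 liver row gives conflicting instructions, hold or reduce the dose again, for an AST/ALT elevation that does not improve while both drugs are on hold

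*Protocol*

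**What the plan says.** Protocol Section 6.7, Table 6, has a row for liver function tests. The trigger in question is "Grade 2 AST or ALT with symptoms OR Grade 3 to 4 AST or ALT elevation". After a check for other causes, the row sets out three steps:

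1. Hold: "Hold both RMC-4630 and sotorasib until the event recovers to Grade 1 or within normal limits or returns to baseline".
2. Restart: "then dose reduce RMC-4630 and sotorasib to one dose level lower".
3. Further step: "If AE does not improve or recurs, dose reduce another dose level".

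A note adds that a subject who started on sotorasib 240 mg has only one reduction available. The row has one mandatory stop: "Both components of study treatment should be permanently discontinued for concurrent elevation of AST or ALT", when bilirubin or INR is also raised and neither cholestasis nor another cause explains it. For severe liver injury with another cause, it offers lower dosing or discontinuation as options. Section 6.7.6 repeats both provisions.

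Two other sections bear on the same events. Section 8.4 counts as a potential DLT in Cycle 1, if related, "Grade 3 AST or ALT elevation lasting >5 days or Grade ≥ 4 AST or ALT elevation of any duration", and sends a run-in subject with a DLT back to Tables 6 and 7. Section 7.1 lists a Grade 4 AE, in a subject who is not withdrawn from the study, among the circumstances in which study treatment must stop.

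**The concern.** Step 3 gives one action to two different situations. A recurrence happens after recovery and restart, so a further reduction fits it. Failure to improve happens before recovery, when steps 1 and 2 have not yet allowed any dose. Telling a site to go down another level at that point contradicts the hold.

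Subject safety is the main thing at stake. Protocol Section 2.2.2.2 names rises in AST and ALT as key sotorasib risks to monitor, and Section 2.2.2.3 names hepatotoxicity among the risks of the combination.

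There is a smaller reporting consequence. SAP Section 7.7.3 tabulates events leading to interruption, reduction and discontinuation separately, so the table in which a given liver event appears depends on how the row was read.

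There is also a narrow route into the run-in decision. A related, symptomatic Grade 2 elevation in Cycle 1 becomes a DLT under Section 8.4 if a drug is permanently discontinued, or if Cycle 2 starts more than 2 weeks late. It does not become one by those criteria if dosing simply resumes at a lower level.

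**Working it through.** No formula applies, and the plan gives no figure to reproduce. The check follows the row's branches and then looks for a resolution elsewhere.

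**Branches of the liver row (isolated AST/ALT elevation)**

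- *Recovers on hold.* Step 2 applies and both drugs restart one level lower. Coherent.
- *Recurs after restart.* Step 3 applies and the dose goes down again, within the limit for sotorasib 240 mg. Coherent.
- *Does not improve.* Step 2 has not been reached because its condition is unmet. Step 1 says to keep holding, while step 3 says to reduce the dose again. Both cannot be followed.

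**Does another provision decide the third branch?**

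- *The row's mandatory stop and Section 6.7.6.* Both need raised bilirubin or INR as well. Neither covers an isolated AST/ALT elevation that stays up.
- *Section 8.4.* It refers the site back to Tables 6 and 7, which is circular.
- *Section 6.7, cap on reductions.* It says what happens to a component once its permitted reductions are used up. It does not say what to do with a subject still on hold.
- *Table 7.* It is for all other AEs. Its Grade 3 entry links a second reduction to re-occurrence only.
- *Section 7.1.* For Grade 4 it says treatment must stop, whereas the liver row says hold and restart lower. That is a second disagreement and does not resolve the one within the row.

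**How the same tables word non-recovery elsewhere**

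- A time limit followed by discontinuation: Grade 3 diarrhea, nausea or vomiting ("If not resolved within 3 weeks, permanently discontinue RMC-4630"); Grade 4 pancytopenia ("If there is no improvement within 4 weeks, discontinue both drugs"); also rash, Grade 3 hemorrhage and febrile neutropenia.
- Non-improvement paired with recurrence: Grade 3 neutropenia, where a further reduction is possible but after a 3-week limit and with discontinuation as an alternative.
- Hold until recovery with no time limit: thrombocytopenia, ocular events, and Table 7 Grades 3 and 4.

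The tables therefore have no single convention. A missing time limit is common and is not itself the defect. What marks out the liver row is that non-improvement under an open-ended hold leads to a dosing instruction.

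**Effect on the run-in table**

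SAP Section 2.3 plans up to 6 subjects at the starting RMC-4630 dose. In Protocol Appendix 11, 1 DLT in 6 evaluable subjects reads escalate and 2 in 6 reads stay. One event classified differently can therefore change the table entry. How likely that is cannot be derived from the documents.

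**Size**

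Protocol Section 2.1.2 gives two sotorasib monotherapy figures: raised AST and raised ALT among the laboratory abnormalities seen in at least 25% of subjects, and serious hepatotoxicity in 3.4%. Applied to the 46 subjects in SAP Section 2.3, these give 46 × 0.25 = 11.5 and 46 × 0.034 = 1.6. They show that the row will be consulted. They are not rates of non-recovery, and the documents give none.

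**The case against.** The best counter-reading rests on the word for a further level in step 3. It presupposes that one reduction has already been made, which happens only after recovery, so the sentence could be confined to subjects already restarted or could set the level for a later restart. Restart is also allowed at Grade 1 or baseline, so some elevation may persist in a restarted subject. This accounts for recurrence but fits non-improvement poorly: a restarted subject has by definition recovered, a later rise is a recurrence, and the row's own Grade 1 line says to continue at current doses. If the reading is accepted anyway, the row has no action beyond an indefinite hold for an isolated elevation that never recovers.

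The protocol also has backstops. Section 6.7 requires Medical Monitor discussion for reductions, caps their number and leaves room for the physician's judgement. Section 7.1 requires discontinuation for unacceptable toxicity and allows it by investigator decision. Section 8 sends immediate safety concerns to the sponsor. These stand, and they make an unexamined re-exposure less likely. They do not tell a site which of the two sentences governs.

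A reader might infer that the row plainly orders re-dosing of an unrecovered subject. The documents do not support that, because the hold sentence is not withdrawn. A reader might also infer that liver-related rates become non-comparable across the roughly 40 sites, or that the efficacy result is affected. The SAP plans no comparison between sites, no hypothesis is tested, and SAP Section 7.6 analyses ORR in the treated population, so these subjects stay in the denominator.

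**Conclusion.** The liver row of Table 6 contradicts itself for symptomatic Grade 2 and Grade 3 AST/ALT elevation without raised bilirubin or INR: an event that has not improved falls under both a hold and a further dose reduction. For Grade 4 there is an additional conflict between the row and Section 7.1. This is an internal inconsistency in a stated safety rule and should be corrected.

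The conclusion rests on one reading, that non-improvement refers to a subject still on hold. That is the natural reading, since restart is conditional on recovery. It rests on no assumed rate. The number of subjects affected is unknown, and no sample size, interval or error rate in the plan changes. The statistical consequence is limited to how individual events are classified in the descriptive safety tables and, in the narrow Cycle 1 case above, in the DLT count.

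It would go too far to conclude from the rows with a time limit that the liver row must adopt one. Other rows have none, and that choice is clinical.

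**What to change.** The sponsor's medical team should reconcile the sentences in the liver row so that two situations have separately stated actions: an event that has not recovered while treatment is on hold, and an event that recurs after restart. The action for the former should not contradict the condition for restarting. The row should then be made consistent with Sections 6.7, 6.7.6, 7.1 and 8.4, including which provision governs Grade 4. The choice of action and of any time limit belongs to the sponsor.

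The cost is a sentence or two in Table 6, any matching cross-references, and a clarification to sites, with the ethics committee approval that Appendix 1 requires for amendments. No analysis in the SAP needs to change.

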6.7.1. Supportive Care Guidelines for Selected Expected Toxicities

Dose modification guidelines for RMC-4630 and sotorasib are summarized in [Table 6](#) and [Table 7](#). Toxicities known from the administration of sotorasib can be found in the current Sotorasib IB. In general, AEs should be managed per institutional guidelines, if available, and should include evaluation for all potential underlying causes. Appropriate subspecialty consultation should be sought, as clinically indicated. The investigator or treating physician should use his/her best medical judgement for management. Guidelines for selected toxicities are summarized below.

6.7.2. Management of Rash

For cutaneous changes suspicious of erythema multiforme or Stevens-Johnson syndrome (SJS), hold all study interventions, treat as per institutional guidelines, and consider dermatology consultation.

For maculopapular rash or perifollicular eruptions, emollients alone may be used for Grade 1 AEs. For Grade 2 AEs, addition of antihistamines and/or topical corticosteroids and/or oral minocycline or doxycycline may be considered. For Grade >2 events, oral steroids may be required.

For dry skin, alcohol-free emollients and soap substitutes should be considered. For folliculitis or cysts, soap substitutes and topical or oral antibiotics are recommended. Consider surgical excision for symptomatic, uninfected cysts. For an erythema-nodosum type rash, emollients, topical steroids, and analgesics are recommended. In more severe cases, dermatologic evaluation, and systemic steroids and/or may be required.

Consultation with a dermatologist should be considered as clinically indicated, including worsening or refractory symptoms, or rapidly growing lesions.

6.7.3. Management of Diarrhea

Evaluate for other or concomitant causes, including medications (eg, stool softeners, laxatives, antacids), infection, including *Clostridium difficile*, malabsorption/lactose intolerance, fecal impaction, and dietary supplements high in fiber.

Premedication for management of diarrhea will be allowed after, but not before, the first dose of study treatment. Premedication should be administered as directed by the investigator.

For Grade 1 or 2 diarrhea, dietary modifications should be considered, including cessation of lactose-containing products, eating small meals, and adequately hydrating. Consumption of the banana, rice, apples, and toast (BRAT) diet may be helpful. In addition, loperamide or codeine may be used or alternatives in refractory cases, such as octreotide and budesonide.

For \geq Grade 3 diarrhea, consider hospitalization for fluid and electrolyte replacement and antibiotics, particularly if accompanied by fever or Grades 3-4 neutropenia.

Consultation with a gastroenterologist should be considered, particularly for severe or refractory cases.

6.7.4. Management of Ophthalmologic Complications

The causal relationship between a change in vision and the study treatment should be carefully explored and an ophthalmologist should be consulted. Immediate consultation should be sought for Grade >1 visual changes. Special attention should be given to macular findings (with optical coherence tomography [OCT] utilization) or retinal vein abnormalities (eg, RVO). If consultation cannot be obtained within 7 days of onset, interrupt all study interventions until the consultation has occurred.

If RVO is diagnosed, permanently discontinue study treatment immediately and treat per institutional guidelines. If uveitis is diagnosed, withhold study treatment, and consider use of topical steroids until resolution. If central serous retinopathy or neurosensory retinal detachment is diagnosed, withhold all study interventions until symptoms resolve and retinal exam shows resolution.

There were no reported cases of retinopathy in RMC-4630-01. However, symptoms of retinopathy were observed in 6.7% (7/104) of subjects, of whom one experienced photopsia and 6 experienced blurred vision. Therefore, subjects treated with RMC-4630 should be monitored for retinopathy. Symptoms include blurred vision, altered color perception, shadows, light sensitivity, metamorphopsia, and glare. Ophthalmic examination by best corrected visual acuity (BCVA), pinhole vision, and OCT are key (refer to Common Terminology Criteria for Adverse Events [CTCAE], v5.0, for grading; note that the grades are based on BCVA).

The onset of retinopathy may occur very soon after dosing (eg, hours to weeks), and may also resolve spontaneously over time. For significant declines in visual acuity, dose hold according to [Table 6](#) until improvement, then restart at the next lower dose level. Ophthalmology (eg, retinal specialist) consultation should be considered, if clinically indicated.

6.7.5. Management of Hypertension

Early identification and treatment of hypertension is recommended. Evaluate for other or concomitant causes. Assess renal function as well as urinalysis. For recurrent or persistent Grade 2 hypertension (systolic blood pressure 140-159 mm Hg or diastolic blood pressure 90-99 mm Hg) treat according to institutional guidelines with the goal of therapy to reduce blood pressure to \leq Grade 1. Hypertension associated with life-threatening consequences (eg, malignant hypertension, neurological deficits, hypertensive crisis), permanently discontinue study treatment. Provide supportive care per institutional guidelines.

Cardiology or nephrology consultation should be considered, as clinically indicated.

6.7.6. Management of Liver Function Abnormalities and Hepatotoxicity

Monitor liver function tests (LFTs, which include ALT, AST, and total bilirubin) prior to the start of the study, weekly during Cycle 1, Day 1 and Day 15 during Cycle 2, Day 1 every Cycle starting at Cycle 3, and at EOT/EOS or as clinically indicated, with more frequent testing in subjects who develop transaminase and/or bilirubin elevations. Assess whether metastatic disease to the liver is contributing to liver function abnormalities and/or hepatotoxicity. Evaluate for infections or other causes of increased liver function abnormalities if appropriate. Consider imaging of the liver. Concomitant medications that may potentiate hepatotoxicity or metabolized by the liver should be held or reduced and the extent of liver injury should be evaluated (eg, albumin level, PTT, or INR).

Concurrent elevation of AST or ALT $>3 \times$ ULN **AND** total bilirubin $>2 \times$ ULN or INR >1.5 in the absence of cholestasis and other causes (eg, viral hepatitis, other pre-existing or acute liver disease, or another drug capable of the observed injury), which may indicate severe drug-induced liver injury (DILI) (possible Hy's law case). Study Treatment should be permanently discontinued.

If liver injury is due to other causes such as viral hepatitis, acute liver disease, or another drug capable of liver injury, evaluate the extent of liver injury (eg, albumin level, PTT, INR, etc) and if considered to be severe, either consider a lower dose for both components of study treatment or discontinue one or both components of study treatment.

Hepatology consultation should be considered, as clinically indicated.

6.7.7. Management of Hemorrhage

Evaluate complete blood count (CBC) and coagulation laboratories. Transfuse blood products and correct coagulation abnormalities as per institutional guidelines. Hold all study interventions if hemorrhage associated with thrombocytopenia, reduced platelet count from baseline, or at the discretion of investigator.

